3.2 Scientific justification of study population

The schools' teachers and students are at increased risk for disease transmission, particularly during disease outbreaks (Wolf *et al.* 2018). Improved water access and hand hygiene are essential to maintaining a hygienic environment for controlling infectious disease transmission in schools (Robinson 2001). In addition, schools are well positioned in principle to implement equitable and sustainable health-related behaviour changes that track from childhood to adulthood (Moore *et al.* 2015).

In Nigeria, it was reported that 70% of the schools lack hygiene services and 43% of them lack sanitation services (UNICEF & WHO 2022). A recent study also showed that there is a significant WASH inequality between private and public schools in Nigeria (Wada *et al.* 2022). None of the public schools included in the study (5 schools) provided any sanitation or hygiene services whereas the other 5 private schools provided both services. The authors of the study indicated that there is a need for sustainable WASH interventions engaging local community stakeholders to facilitate the narrowing of existing inequalities (Wada *et al.* 2022).

The overcrowding conditions in the schools where the average number of students per elementary class ranged from 51 to 101, along with the humanitarian crisis urge the need for targeting these schools with sustainable interventions promoting WASH services and hand hygiene. The targeted schools in H4H project lie around Maiduguri, the capital and the largest city of Borno State in north-eastern Nigeria. The humanitarian needs are increasing in all locations in Borno state due to escalating crisis between the Boko Haram group and the Nigerian army, however, many places like the Mafa refugee camp are hardly or not accessible due to deteriorated security. The focus has been shifted to the schools around Maiduguri, which are likely to remain accessible.

In a different fragile setting, a long-lasting military occupation in Palestine created an unstable and coercive humanitarian environment that left a lot of schools, specifically in Area C, deprived of basic water and hygiene services. According to the JMP report, basic hygiene services are available in only 21% of the schools in Palestine (UNICEF and WHO 2022). There are 3 types of schools in Palestine; public, private and UNRWA⁵-administered. The schools lie in Area C are either public or under the administration of UNRWA. The latter type lies in refugee camps that are completely under the supervision of UNRWA. The project targets public schools in remote and rural areas in Area C that are most in need for WASH services improvement. The average number of students per elementary class in these schools is about 30. Usually, in such schools any improvement to WASH sector is challenging due to restrictions on infrastructure rehabilitation imposed by the Israeli military occupation.

The H4H project primarily addresses such contexts where WASH services are inadequate, and large investments for the improvement of infrastructure are unlikely in the near future. This is the case in many conflict areas, refugee and internally displaced population camps,

⁵ UNRWA is The United Nations Relief and Works Agency for Palestine Refugees in the Near East

informal settlements and remote rural areas with poor or failed institutional structures. Within this project schools located in such contexts are targeted to implement the H4H MCI.

Tdh and Cesvi have established offices in Nigeria and Palestine supporting health and WASH interventions in schools. Tdh and Cesvi collaborate closely with local authorities and the most relevant stakeholders who expressed their support for this project.

4 STUDY DESIGN

The overall project will follow a multi-center cluster-randomized controlled trial (cRCT) design (Figure 2). Prior to this study, a group of schools in the study's target areas were surveyed by the Tdh (in Nigeria) and Cesvi (in Palestine) using the Facility Evaluation Tool for WASH in Schools ([FACET WINS](#)) which is a monitoring tool for WASH delivery services in schools. From these schools a subsample was identified which fulfils certain inclusion criteria (for the inclusion criteria see chapter 5.2 Inclusion criteria).

This subsample was handed over to the local Tdh and Cesvi collaborators who carefully assessed the security situation around the schools. The Tdh and Cesvi collaborators then selected 26 facilities per country, which are most probable to still be accessible for data collection within the next year. These 26 schools will then be allocated to the two arms (intervention vs. control) with covariate constrained stratified randomization using computer-generated randomization code provided by a statistician not involved in any field activities. The intervention arm will receive the full intervention package (handwashing station, behavioural change intervention, capacity development, and management support). The control arm will receive nothing for the duration of the intervention (12 months). Afterwards, they will receive the same intervention package with potential improvements identified in the former intervention group.

In the selected schools, 50 eligible students from each school will be selected from one or two classes within the age group (10-12 years) using random sampling. If the school has at least one class that has ≥ 50 students within the target age group, the sample will be selected from that class, otherwise, the sample can be selected from two classes. For module 1, only 25 students of the 50 students included in the study in each school will be involved. For module 2, the 50 students included in the study in each school will be targeted for assessment using this module. For Module 3, 12 students out of the 25 students targeted with assessment using module 1 will be targeted for assessment using this module.

Module 4 follows the sample size calculation of the cRCT design, hence 50 students from each of the 24 schools will be monitored. For module 5 which is only restricted to students from Palestine, the same sampling plan of the cRCT will be used, and the sample size will be the one foreseen to fulfil the main study objectives. For Module 6, 10 FGDs (including students) and 5 FGDs (including teachers) will be administered and for Module 7, 10-20 interviews.

[figure not shown]

Figure 2: Consort flow diagram of the schools selection for the H4H cRCT in Nigeria

The methods to achieve the different objectives of this project are summarized in Table 1. These modules will include qualitative and quantitative data approaches in order to enable a triangulation of the overall project results. The following modules will be used in the cRCT and the overall project: (i) Module 1: Combined RANAS and well-being survey, (ii) Module 2: Structured handwashing observations, (iii) Module 3: Microbiological analysis of hand rinse samples, (iv) Module 4: Diary approach for health outcomes and absenteeism, (v) Module 5: personal, physical and social contextual factors survey (vi) Module 6: Focus Group Discussions (FGDs) and (vii) Module 7: Key informant interviews (KIIs).

Table 1: Overview of different project modules and analysis by objective

Module	Objective	Analysis
Module 1: Combined RANAS and well-being survey	
PO: Evaluate the effects of the H4H MCI on hand hygiene of primary school students in Nigeria and Palestine
 
SO1: Evaluate the effects of the H4H MCI on the well-being of primary school students in Nigeria and Palestine
 
SO2: Assess the effect of the H4H MCI on hygiene-related RANAS behavioural factors of primary school students
	
 - Descriptive statistics and multiple random effect regression models
Module 2: Structured handwashing observations	PO: Evaluate the effects of the H4H MCI on hand hygiene of primary school students in Nigeria and Palestine	
 - Descriptive statistics, multiple linear regression models and logistic regression models
Module 3: Microbiological analysis of hand rinse samples	PO: Evaluate the effects of the H4H MCI on hand hygiene of primary school students in Nigeria and Palestine	
 - Analysis of E. coli and total coliforms - Descriptive statistics, multiple linear regression models
Module 4: Diary approach for pre-defined health outcomes and absenteeism	EO1: Evaluate the effects of H4H MCI on health outcomes and absenteeism	
 - Descriptive statistics
Module 5: personal, physical and social contextual factors survey	SO3: Explore the associations of personal, physical and social contextual factors with hand hygiene and well-being of primary school students in Palestine	
 - Descriptive statistics, multivariate regression models
Module 6: Focus Group Discussions	SO4: Explore the perceived impacts of the H4H MCI on the health and well-being of primary school students	
 - Framework methodology
Module 7: Key informant interviews	SO4: Explore the perceived impacts of the H4H MCI package on the health and well-being of primary school students	
 - Framework methodology

Local collaborators from Tdh and Cesvi and the regional Ministries of Education (MoE) were involved from the study's kick-off meeting onwards and are regularly being consulted in bi-weekly meetings and additional ToC workshops led by Skat Foundation. The data collection methods for each module will be described in further detail:

Module 1: Combined RANAS and well-being survey: The survey will be developed through the RANAS approach and will not only include attitude and belief questions, but also target the underlying psychological factors postulated by the RANAS model that are important precursors for effective behaviour change (Mosler and Contzen 2016). If needed, this survey will be enriched with additional questions to assess the knowledge and self-reported handwashing practices of the participants. The well-being of the students will be assessed in the survey using the KINDL tool (Ravens-Sieberer and Bullinger 1998). It is a tool designed to measure health-related quality of life in children and adolescents by looking into different domains of well-being (e.g. physical, mental and school) (Ravens-Sieberer and Bullinger 1998). The perceived sufficiency and safety of the water supply, satisfaction with the available infrastructure for handwashing, and obstacles to water access will be also assessed. The survey will be administered to primary school students three times in total; as a baseline survey before the intervention package, about three months after the intervention and about a year after the baseline survey with the software Open Data Kit (ODK) Central (version 2022.3.1) on Android tablets. Informed consent forms will be obtained from the participants' guardians before the day of data collection. In addition, oral assent will also be obtained from the participants at the beginning of the interview for filling out the survey.

Module 2: Structured handwashing observations: Structured handwashing observations are perceived as a gold standard method to assess handwashing behaviour in schools (Pickering *et al.* 2013; Caruso *et al.* 2014; Dreibelbis *et al.* 2016; La Con *et al.* 2017; Parkinson *et al.* 2018). Data from Module 1 and the observations can later be combined through a unique ID of the study participants. The observations will be administered with students three times at the same time points as the survey in Module 1. To be able to assess individual behaviours and link them to data collected using other tools, all eligible students in the classes selected for the study will be assigned coloured badges with their unique IDs. Students will be informed that they are randomly assigned the colours. However, the data collector will agree with the school teachers on a specific colour to be assigned for the 50 selected students for the study. The observation will start at 9:00 am (60 minutes before the breakfast break) and end at 12:00 pm (90 minutes after the break). The data collector will pilot the observation process before the intervention and in coordination with the school staff.

The occurrence of handwashing with soap will be observed for each of the two critical handwashing events (after using the toilet and before eating) for each included student. The occurrence of handwashing before eating (our primary outcome) is an opportunity that could be observed once for all students when break time starts. The break time included in the observation period is the first break for all students during a school day, and all of them use it for eating their brunch (as confirmed by the local teams). No matter where the station is they are expected to come and wash their hands before eating. For observing the occurrence of the other critical event and if the station was not located next to toilets, we would have two observers; one is next to toilets and the other one is next to the stations. Both would observe and then compare their results. The observations will result in a dichotomous measure, i.e. if the handwashing with soap for each critical event occurred or not. However, there will be choices like "was not visible" or "soap or water was not available" to take into consideration the complicated conditions in the field.

If the opportunity for handwashing before eating was not possible for all students, an alternative scenario is proposed. In the class before the break, students will be engaged for 30 minutes in painting activity. At the end of the activity and as a reward, students will be provided with a popcorn snack and will be given free time of 15 minutes so they can eat together the snack. They need to use their hands for eating the popcorn, so, they are expected to wash their hands before eating it. They will also be told they can go outside the classroom if they want so they would be left with the choice to wash their hands before eating if they want. During that time, one observer will be standing close to the handwashing stations (or water points before installing the Grav't'eau) and recording all the students who take the

opportunity and wash their hands before eating and any other handwashing opportunity, e.g. after using the toilet. The observation will continue during the break time (45 minutes) so as to cover all opportunities for handwashing before eating for students who opted not to eat the snack and want to have lunch during the break. Students will be asked to keep the badges until the end of the activity. Other handwashing opportunities will be also recorded.

Also, if it was feasible the steps of handwashing will be observed for the students who wash their hands.

Consent for observation will be obtained at a school level, from the principal of the school, as well as from the parents.

Module 3: Microbiological analysis of hand rinse samples: Hand rinse samples of students will be collected after administering the survey with a modified glove juice method as described by Pickering *et al.* 2010. First, the enumerators will visually assess the cleanliness of the participant's hands with an observation form prompting for visible dirt in different areas of the hands, such as the thumb and under the fingernails (Contzen *et al.* 2015, Pickering *et al.* 2010 (b)).

For the hand rinse sample collection, the enumerators will have to wear sterile gloves. The participant's randomly selected hand will be inserted into a 69-oz Whirl-Pak bag (NASCO Corp., Fort Atkinson, WI) filled with 350 mL of clean water. Then, the participant has to shake her/his hand in the water and rub her/his thumb and fingers together for 15 seconds. Afterwards, the enumerator will massage the participant's hand through the bag for another 15 seconds. The participant will be provided with a paper towel to dry the hand, once it is retrieved from the bag (Pickering *et al.* 2010 (b)). Afterwards, the procedure will be repeated with the other hand.

The Whirl-Pak bags containing the samples will be kept on ice in an isolation box and processed within 4 hours of sampling (Pickering *et al.* 2010 (b)). Membrane filtration will be used to detect colony-forming units (CFUs) of *E.Coli* and total coliforms. In a field laboratory, the content of the bags will be passed through a 47-mm-diameter 0.45 µm cellulose filter. The filter paper will then be placed on growth media and incubated at 35°C ± 0.5°C for a duration of 24 hours for *E.Coli* and total coliforms (Pickering *et al.* 2010 (b)). We plan to filter 100 mL per bag to detect CFUs of *E.Coli* and total coliforms. The exact amount of mL will be established during piloting as the volume used is dependent on the degree of bacterial contamination on the hands. Compact dry plates will be used for the detection of *E.coli* and total coliforms.

The lower detection limit of CFUs will be calculated by dividing 1 CFU/plate by the filtrate volume and then multiplying it with the total Whirl-Pak volume of 350 mL. The upper detection limit will be calculated by dividing 500 CFUs/plate by the filtrate volume and then multiplying it with the Whirl-Pak volume. For the statistical analysis, the CFUs per hand will be normalized and \log_{10} transformed (Pickering *et al.* 2010 (b)).

Module 4: Diary approach for pre-defined hygiene-related health outcomes and absenteeism incidence: Longitudinal data on hygiene-related health outcomes and absenteeism will be collected over the study course (12 months) in both arms of the study. The main outcome of this objective is students' hygiene-related absenteeism. Absenteeism is hygiene-related if the student suffered from diarrhoea, respiratory tract infections, helminth infections, head lice, trachoma and skin infections. For the outcome of this objective an electronic/paper diary will be prepared by the PhD and used in each school by one of the teachers on a daily basis to report the absenteeism of included students in each cluster along with the reason for their absenteeism (pre-defined health outcomes). To adjust for the cluster design effect, we will calculate the rates of hygiene-related absenteeism separately for each medical reason for each school. This will be carried out by dividing the number of episodes of hygiene-related absenteeism for each medical reason by the number of student-weeks. The

answer will then be multiplied by 100 to obtain rates per 100 student-weeks and will be presented using descriptive statistics.

Module 5: personal, physical and social contextual factors survey: Handwashing behaviour and well-being of school children are not only influenced by the level of water access and psychosocial behavioural factors but also depend on culture- and context-related factors. The exceptional stressors forced by the prolonged military occupation in Palestine result in difficult personal, social and physical conditions which lead to disruption in different aspects of life beyond the school environment. The analysis of all possible determinants of hand hygiene behaviour and well-being at baseline before the start of the intervention will provide a better understanding of factors that potentially modify the effectiveness of an intervention and may need consideration for maximising effectiveness on hygiene and well-being when implementing larger-scale WASH interventions in the Palestinian context.

The study design will be baseline cross-sectional. This objective will be fulfilled through the baseline assessment conducted before randomising the recruited schools in Palestine into the two arms of the study. The assessment will be carried out through a survey that is self-reported by the parents of the students in the selected classes for the study. The survey will include questions related to the availability of hygiene services at the household level, evaluation of parents' hygiene knowledge and behaviour, and assessment of their child's hygiene behaviour as reported by them.

Module 6: Focus Group Discussions: The FGD is a rapid and resource-efficient method of gathering information since all the target participants and the researcher are readily available at the same study site (Mack *et al.* 2005; Nyumba *et al.* 2018). There is no need to collect participants from different environments and prepare them in advance, rather, they will be met in their usual studying environment which also helps not to introduce their expectations and biases, including strategic group bias (Nyumba *et al.* 2018). Also, the concentrated nature of the FGD avails a large quantity of data in much less time usually needed to collect an equivalent number of interviews (Nyumba *et al.* 2018).

10 gender-separated FGDs will take place in the included schools in the intervention arm; 5 FGDs for each gender in autumn 2023. However, the saturation factor⁶ will be considered when conducting the discussions in the field. Each group will include students of the same age of the age group target (10-12) to avoid any domination of older students if the groups include different age groups. Using separate groups for boys and girls will help ensure meaningful feedback since children may feel shy speaking in front of each other and usually there is an increase in teasing among children at the age of 10 (Dzino-Silajdzic 2018). It is important for them to feel comfortable speaking their minds freely and not feel shy, embarrassed or worried someone will make fun of them (Dzino-Silajdzic 2018). Each FGD will be composed of 5-8 selected students. The selection of the students will be consulted with the school administration, however, selected students need to represent each participating class in the intervention arm of the trial.

Additionally, there will be 5 FGDs composed of 5-8 teachers from included schools in the intervention arm. The teachers invited to participate in the FGDs should be permanent employees in the school and teach the classes included in the intervention.

Data will be collected by a small local team with experience in qualitative data collection and if the security situation allows, the PhD student would join the team. The team will be composed of at least a moderator and a note taker who is trained prior to data collection by the PhD student. A field research journal will be used throughout the data collection to take structured notes and observations of the FGDs. The discussions will be tape-recorded and then transcribed in the local language and translated into English for further analysis.

⁶ Saturation is reached when answers of participants start repeating and no new information can be gained through additional FGDs.

Field notes, observation notes and focus group transcripts will be analysed using the framework method with the software MaxQDA (VERBI Software, Marburg, Germany) or NVivo (QSR International, Melbourne, Australia) (Gale *et al.* 2013).

Module 7: Key informant interviews: The key informant interviews target stakeholders in the Ministry of Education, school committee and leaders of the community to help solicit a different kind of information that is deeper and more detailed about the nature of the problems and recommended solutions. These insights help in the triangulation of data and could not be gained through the FGDs as the group dynamic may not allow for asking probing and in-depth questions (Kumar 1989). Also, having stakeholders in the FGD may prevent other participants from voicing their opinions (Mack *et al.* 2005). The KIIs will take place in autumn 2023.

Interviewers will receive the same training as for the Focus Group Discussions. The interviews will be audio recorded and then transcribed into the local language and translated into English for further analysis. In some instances, interviews may be carried out remotely (online) from Switzerland, in English, if it is appropriate. They will be audio recorded, transcribed, and translated if necessary for further analysis.

As the FGD transcripts, the interviews will be analysed using the framework method with the software MaxQDA (VERBI Software, Marburg, Germany) or NVivo (QSR International, Melbourne, Australia) (Gale *et al.* 2013).

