capacity of managing WASH services adequately (UNICEF and WHO 2022). Therefore, it is crucial to concentrate efforts on providing adequate WASH services in such contexts by targeting school staff and students with sustainable interventions that improve their level of water access and hand hygiene behaviour, also given that children in these schools likely also have no or very limited hand hygiene resources at home and in their family environment. The Hands4Health (H4H) project primarily addresses such contexts where WASH services are inadequate, and large investments for improvement of infrastructure are unlikely in the near future. This is the case in many conflict areas, refugee and internally displaced population camps, informal settlements and remote rural areas with poor or failed institutional structures. Within this project schools located in such contexts in Nigeria and Palestine are targeted to implement the H4H Multi-Component Intervention (MCI).

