4.1 Primary endpoint

The main aim of the intervention is to improve hand hygiene. So, hand hygiene will be assessed in this study by assessing the occurrence, frequency and technique of handwashing behaviour using different tools. We will operationalise our target behaviour in this study as handwashing with water and soap at two critical events: (i) after using the toilet and (ii) before eating. However, the primary outcome in this study is the occurrence of handwashing with water and soap before eating during 3-hours observation for one day. It is selected as the primary outcome since it could be objectively assessed for all included students during the break whether because they have the opportunity since they eat their brunch during the break, or because they will eat a snack provided to them on the day of data collection.

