9.3 Participant information and consent

The Investigator or his/her representative will explain the nature of the study to the participant's guardian and the participants according to the guidelines referred to, and answer all questions regarding this study, prior to obtaining informed consent.

In both countries, the Ministry of Education (MoE) permits written consent from the participant's guardian and oral assent from the children. This approach is adopted to prevent potential confusion among parents/guardians that may arise from seeking written assent. The ethics committees in both countries have granted approval for the consent form to be signed by the participant's guardian, accompanied by oral assent from the children.

In the case of an illiterate participant's guardian, an impartial witness will be called to make sure that the participant's guardian understood the information and agrees. This witness must be independent of the research being conducted and cannot be influenced unfairly by the researchers. For example, a literate relative of the participant's guardian is eligible as an impartial witness. Both, the participant's guardian and the impartial witness must sign the ICF. If the participant's guardian does not have a signature, a fingerprint will be sufficient.

For the handwashing observations, the survey and hand-rinse samples, the participants' guardians will be asked for consent at least two weeks prior to data collection. Their written consent will be sought without letting them know when exactly the observers and enumerators will visit the school. For the handwashing observation, oral assent of children will be sought retrospectively at the end of the project.

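### Teachers in both arms are told which badge colour marks the 50 pupils who supply the primary outcome, and nothing prevents or records prompting on the observation day

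*Combined protocol and SAP*

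**What the plan says.** Section 4.1 defines the endpoint: "the primary outcome in this study is the occurrence of handwashing with water and soap before eating during 3-hours observation for one day". Section 4 names who supplies it: "For module 2, the 50 students included in the study in each school will be targeted for assessment using this module".

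Module 2 in Section 4 explains how these pupils are recognised. Badges go to more pupils than the sample: "all eligible students in the classes selected for the study will be assigned coloured badges with their unique IDs". Pupils get a neutral explanation: "Students will be informed that they are randomly assigned the colours". Teachers are told more: "the data collector will agree with the school teachers on a specific colour to be assigned for the 50 selected students for the study". School staff are also involved at the pilot stage: "The data collector will pilot the observation process before the intervention and in coordination with the school staff".

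The safeguards are aimed at others. Section 4.3 keeps pupils unaware of the observation and the observer at a distance. Its blinding statement says that participants, data collectors and the statistician cannot be blinded, and does not mention teachers. Section 9.3 withholds the visit timing from guardians: "Their written consent will be sought without letting them know when exactly the observers and enumerators will visit the school". No matching rule is given for teachers.

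**The concern.** The outcome is a behaviour that an adult can trigger with one remark just before the break. Whoever knows which pupils are scored can raise the score without any lasting change in habit. All badge wearers carry an ID, so the colour is what visibly separates measured from unmeasured pupils.

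Teachers in intervention and control schools receive the same information. Any difference between arms must therefore come from what they do with it. Intervention schools have the new or repaired facilities, the behaviour change activities, and staff training and support (Sections 2.3.1 to 2.3.5). Control schools receive nothing for 12 months (Section 4). Section 4.3 itself expects that local people may wish to please the implementing organisations, but raises this only for the Module 1 survey. It is a reasonable inference that prompting is likelier in intervention schools.

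If so, the measured difference would mix the effect of the package with reminders given for the visit. The primary model has intervention as its only predictor and a random effect for school (Section 6.3). Prompting is not recorded, so the analysis could not separate the two.

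**Working it through.** **1. Is there any control on teachers?** The places to look are the Module 2 text in Section 4, the bias measures in Section 4.3 and the consent procedure in Section 9.3. None keeps teachers unaware of the colour, asks them not to prompt, or provides a field for prompting.

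**2. Where does the colour add information?** Section 3.2 gives average class sizes of 51 to 101 in Nigeria and about 30 in Palestine.
- Nigeria, two classes as in Section 5.2: 102 to 202 pupils, so the 50 are 50/202 = 25% to 50/102 = 49%.
- Nigeria, one class of at least 50 as in the general rule of Section 4: 50/101 = 50% to 50/51 = 98%.
- Palestine, two classes: about 60 pupils, so 50/60 = 83%. Prompting the whole class would act almost the same way as prompting the marked pupils.

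These shares use all enrolled pupils. Among eligible badge wearers they would be higher.

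**3. The plan's own figure.** Section 6.2 assumes 20% against 45%, ICC 0.2, 50 pupils per school, 80% power and 95% confidence (read as two-sided 5%).
- Pupils per arm without clustering: (1.960 + 0.842)² × (0.20×0.80 + 0.45×0.55)/0.25² = 51.2.
- Design effect: 1 + 49 × 0.2 = 10.8.
- Schools per arm: 51.2 × 10.8/50 = 11.05; adding one for the small number of clusters gives 12.05, so 13.
- A beta-binomial simulation with a school-level t-test gives 78.5% power with 12 schools and 81.6% with 13.

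The stated 13 per arm is reproduced, so the same set-up can be used below.

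**4. Illustration with no true effect.** Let p0 be the washing rate in both arms without prompting, and b the rise produced by prompting in intervention schools only, so p1 = p0 + b. The documents give no value for b. The 10% rate is also an assumption.

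SE = √{[p0(1−p0) + p1(1−p1)] × (0.2 + 0.8/50)/13}, and the error rate comes from a two-sided noncentral t with 24 degrees of freedom and noncentrality b/SE.

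| p0 | b | Pupils per school (50b) | SE | b/SE | Two-sided error |
|---|---|---|---|---|---|
| 0.20 | 0 | 0 | 0.0729 | 0 | 5.0% |
| 0.20 | 0.05 | 2.5 | 0.0760 | 0.658 | 9.7% |
| 0.20 | 0.10 | 5 | 0.0784 | 1.275 | 23.2% |
| 0.10 | 0.05 | 2.5 | 0.0601 | 0.832 | 12.6% |
| 0.10 | 0.10 | 5 | 0.0645 | 1.552 | 31.9% |

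**5. Cross-check by simulation.** Suppose prompting converts a share q of the non-washers in intervention schools, with 20% washing otherwise. At q = 10%, 0.8 × 0.10 × 50 = 4 pupils per school change. The chance of a false significant benefit rises from 2.5% to about 20% with 13 schools per arm. It is about 36% with 26 per arm, which applies if the 26 schools per country in Section 4 are pooled. If the ICC of 0.2 is on the latent logistic scale, the 13-school figure is about 31%.

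Steps 4 and 5 use a school-level comparison in place of the planned logistic mixed model. They show how sensitive the result is to a bias of a given size, not how large the bias is.

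**The case against.** **The colour is not the only route.** One teacher per school keeps the daily Module 4 diary on the included pupils, and teachers are consulted on attendance for an exclusion criterion (Section 5.3). Deleting the agreement would not hide the sample fully. This stands, and it is why the remedy must also cover instruction and recording. Still, a list held by one teacher discloses less than a visible colour agreed with the teachers.

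**The direction is inferred.** A reader might conclude that the outcome rises in one arm only. The documents do not support that: the disclosure is the same in both arms, and control teachers could prompt too. Some routine reminding may also belong to the package, whose behaviour change techniques are not yet listed (Section 2.3.3). Only prompting tied to the visit is bias.

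**The visit day.** A reader might infer that schools know the exact day. No section says so. Equally, no section says that they do not.

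**The colour serves a purpose.** Observers must recognise 50 pupils from a distance. Reading the ID of every badge wearer who washes could increase the number of observations recorded as not visible, and missing data are not imputed (Section 6.4). This stands, so the fix keeps a colour key but places it with the observers.

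**Other protection.** Pupils are kept unaware of the observation, and bacterial counts are read blind. Neither addresses prompting of the primary outcome.

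**Conclusion.** The point holds as an avoidable disclosure that creates an opportunity for bias in an unblinded primary outcome. It does not show that teachers will prompt, or that the primary result would be invalid. The likely direction is towards the intervention, on the inference that intervention-school staff have more means and reason to prompt. Selective prompting matters mainly in Nigeria. In Palestine, hiding the colour gains little, and the visit window and the no-prompting rule do most of the work.

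The size cannot be estimated from the documents. If prompting added 5 or 10 points in intervention schools only, the two-sided error rate would be about 10% or 23% under the plan's own 20% control rate, ICC and sample size. Any bias of that size would give the same figures, so they say nothing about how likely prompting is. This is a cheap improvement that should be made before observations begin. The sample size, endpoint and model need no change.

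**What to change.** In Section 4 (Module 2), with matching text in Section 4.3:

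1. Delete the agreement with teachers on the colour. The study team assigns and hands out the badges.
2. Only the observers hold the colour key, and it changes by school and by round.
3. Instruct staff in both arms, in the same words, not to prompt pupils to wash on the observation morning.
4. Add a tick-box to the observation form for any adult prompt, by pupil or group. Pre-specify a sensitivity analysis of the primary outcome that uses it, for example counting prompted washes as not washed.
5. State that schools receive a visit window and not the exact day.

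The cost is slightly more work for observers when badges are handed out, and one extra form field. Two limits remain. The diary teacher still knows the sample and could match it to the colours, so concealment is partial. Observers can record only prompts that they see or hear, so reminders given inside the classroom before the break may be missed.
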